4.2 ANALYSIS OF STUDY CONDUCT

The number and percentage of patients who were randomized, received treatment, and completed the study will be summarized. For randomized patients, the number and percentage of patients who completed the study and discontinued the study, along with

the reasons for premature discontinuation, will be tabulated overall and by treatment group. A listing of patients who discontinued early from the study will be generated. Relatedness to COVID-19 will be determined by the Sponsor prior to the interim and final analysis in a blinded manner, and included in the listing and the summary.

A summary of the duration of study participation will be produced. Duration in days will be calculated as the last assessment date according to the schedule of study activities minus the randomization date + 1. Categorical summaries of number and percentage of patients who complete each scheduled visit will also be displayed, showing the overall completion as well as a breakdown by mode (in-person, phone or telemedicine). Summaries of missed visits will tabulate relatedness to COVID-19.

The number and percentage of patients included and excluded from the analysis populations (ITT, Safety and PP) will also be tabulated overall and for each treatment group. Reason(s) for exclusion from each population will be summarized. Patients excluded from analysis populations will be listed.

Major protocol deviations will be listed and summarized by treatment group. The summary of exclusions from the PP population will distinguish the major deviations related and unrelated to COVID-19. Relationship of major protocol deviations to COVID-19 will also be listed.

4.3 ANALYSIS OF TREATMENT GROUP COMPARABILITY

Demographic and baseline characteristics such as age, sex, race, ethnicity, baseline mRS, and baseline NIHSS will be summarized for the ITT population overall and by treatment group.

The number of non-missing observations, mean, standard deviation, median, minimum and maximum values of the continuous variables will be summarized by treatment group. Categorical variables will be summarized using numbers and percentages of patients in each category; unknown or missing will be included as a separate category.

Baseline for mRS, NIHSS, vital signs and lab parameters will be defined as the last available assessment prior to initiation of study medication. For patients who do not receive study medication, baseline values will be defined as the last available assessment prior to randomization. These will be included in listings.

4.4 MEDICAL HISTORY

Medical history is collected as general (as open ended response) as well as targeted conditions of myocardial infarction, hypertension, atrial fibrillation, hypercholesterolemia, diabetes, and prior stroke. Open ended responses will be coded using the latest version of the Medical Dictionary for Regulatory Activities (MedDRA) and summarized by system organ class and preferred term. Patients reporting more than one condition/diagnosis

within a body system will be counted only once for that body system. Targeted medical history will be summarized by the pre-specified term. All medical history data will be listed.

4.5 PRIOR AND CONCOMITANT MEDICATIONS

Prior medications refer to those stopped prior to study day 1. Concomitant medications refer to those used by a patient from 7 days prior to initiation of study drug to the study completion/discontinuation visit. These will be coded using WHO (World Health Organization) Drug Dictionary and summarized by medication class and preferred term.

4.6 EFFICACY ANALYSIS

Efficacy analyses will be performed using the ITT population with patients grouped according to treatment assigned at randomization. Available data regardless of adherence to the protocol will be included in the efficacy analyses; this includes data from patients who discontinued prematurely from the study.

Deviation from the AHA/ASA treatment guidelines for standard of care (i.e. mechanical thrombectomy [MT] is planned for the patient but not performed due to various reasons) is considered an intercurrent event in this study. COVID-19 infections are considered another type of intercurrent event. COVID-19 infections during the follow-up period will be captured as AEs. In efficacy analyses, treatment policy strategy will be applied to both COVID-19 and non-COVID-19 intercurrent events. That is, all collected data will be used regardless of the occurrence of these intercurrent events.

Visit windows will be derived according to [Table 2](#) and applied for all clinical efficacy assessments. If there are multiple assessments within the same window, the one closest to the target time point will be used. Assessments that are outside of the defined windows will not be used in analysis, except they may provide a value for the last observation carried forward (LOCF) imputation in the case of mRS (see Section [4.9.1.1](#)).

Table 2 Definition of Visit Windows

Visit	Target Time	Window: mRS, GOS, BI, Neuro-QoL*	Window: NIHSS	Window: imaging
24 hours	24 hours	N/A	18 to 30 hours	18 to 30 hours
72-96 hours	84 hours	N/A	60 to 96 hours	60 to 120 hours
Day 5	5 days	4 to 6 days	5 to 6 days	N/A
Day 30	30 days	15 to 60 days	15 to 60 days	N/A
Day 90	90 days	61 to 120 days	61 to 120 days	N/A

BI = Barthel Index; GOS = Glasgow Outcome Scale; mRS = modified Rankin Scale; Neuro-QoL = Quality of Life in Neurological Disorders; NIHSS = National Institutes of Health Stroke Scale.

* Assessed only at Day 90 Visit

All analyses of efficacy endpoints (primary, secondary, and exploratory) will be evaluated for superiority. Analyses will be adjusted for all or a subset of the following variables:

- Age (≤ 70 vs. > 70 years of age)
- Type of occlusion (ICA/M1 vs. M2)
- Baseline NIHSS (≤ 15 vs. > 15)
- Randomization site (ECC vs. nECC)
- Mechanical thrombectomy planned (Yes vs. No)
- Protocol version (Protocol V1-4 vs Protocol V5).

In order to avoid small number of patients in the resulting strata, some variables may be removed from this list and not be adjusted for. The algorithm to perform this assessment is provided in [Appendix 5](#).

For endpoints that are based on the imaging data where both local and central reader's evaluation are collected, the central reader's evaluation will be used for analysis. Post-baseline final infarct volume will only be recorded by the central reader. The local recording for the baseline image will be used to calculate change from baseline in final infarct growth at 72-96 hours (or discharge if patient is being discharged prior to 72-96 hours visit).

Analyses of NIHSS, BI and GOS will only utilize data collected in-person or by telemedicine. NeuroQoL will only utilize data collected in-person. If any of these assessments are conducted by a mode that is not allowed for the assessment, the data will be listed, but excluded from analysis and not replaced by imputations.

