- ^h A baseline NIHSS will be used to determine stroke severity and study eligibility. This assessment will be performed per institutional practice during hospitalization, upon hospital discharge and at the listed follow-up visits. In the event of an *ICH* event that occurs within 36 hours of drug administration, a NIHSS assessment is *to* be completed. See [Appendix 3](#) for NIHSS. Please refer to [Appendix 7](#) for brain imaging requirements.
- ⁱ Patients will undergo two follow-up MRI scans (*MRI/MRA/MRP at the first follow up and MRI at the second follow up*). Patients who cannot undergo an MRI will undergo a multimodal CT/CTA/CTP at the first follow-up and a non-contrast CT at the second follow-up. The first follow-up scan will be obtained at approximately 24 (± 6) hours after randomization. The second follow-up scan will be obtained at 72–96 hours after randomization. See [Appendix 7](#) for brain imaging requirements.
- ^j See [Appendix 4](#) for the Barthel Index.
- ^k See [Appendix 5](#) for GOS.
- ^l See [Appendix 6](#) for Neuro-QoL.

Appendix 1

Schedule of Activities (cont.)

- ^m Study drug administration needs to occur within 90 minutes of qualifying RAPID brain imaging. If 90 minutes is exceeded, CTP/MRP imaging must be repeated to validate that the patient is still eligible for the study. Study drug administration *is recommended to occur before the start of endovascular therapy (defined as groin puncture)*. If it appears that it will be challenging to administer study drug prior to femoral groin puncture for a planned thrombectomy, *it is recommended that the patient not be randomized. However, if the patient has already been randomized, and due to unforeseen circumstances the drug cannot be administered prior to groin puncture for the planned thrombectomy, the drug must be administered as soon as possible and prior to manipulation of the clot.*
- ⁿ In addition, all medications (e.g., prescription drugs, over-the-counter drugs, vaccines, herbal or homeopathic remedies, nutritional supplements) used by the patient within 7 days prior to initiation of study treatment will be recorded.
- ^o New or worsened clinically significant abnormalities should be recorded as adverse events on the Adverse Event eCRF.
- ^p Activities may be performed at discharge, if discharge is prior to *the 72–96 hour visit. If the patient is discharged within 24 hours of the 24-hour visit, no 72–96 hour visit image collection is required.*

Appendix 2

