 - If CTA (or MRA) is technically inadequate: $T_{max} > 6$ s perfusion deficit consistent with an ICA or M1, M2 occlusion **AND** target mismatch profile (ischemic core volume < 70 mL, mismatch ratio ≥ 1.8 and mismatch volume ≥ 15 mL as determined by RAPID software)
 - If MR perfusion (MRP) is technically inadequate: ICA or M1, M2 occlusion by MRA **AND** diffusion-weighted imaging (DWI) lesion volume ≤ 25 mL for an M1 or ICA occlusion and ≤ 15 mL for an M2 occlusion. If MRA is technically inadequate, a CTA can be used if performed within 60 minutes prior to the MRI. Carotid occlusions can be cervical or intracranial; with or without tandem MCA lesions
 - If CTP is technically inadequate: patient can be screened with MRI and randomized if neuroimaging criteria are met.
- *DSA images: baseline, mechanical thrombectomy, and post thrombectomy images obtained during angiogram to determine the required TICI scores*

24-hour imaging:

- An MRI will be performed 18–30 hours (approximately 24 *hours* [± 6 hours]) post-randomization to assess reperfusion, recanalization, and ischemic core growth. This will include an MRA of the Circle of Willis to assess for recanalization and an MRP study to assess for reperfusion in addition to standard fluid-attenuated inversion recovery (FLAIR), gradient recalled echo (GRE), and DWI sequences per standard of care. At the investigator's discretion, a repeat CTP may be performed at 18–30 hours if MRI is not possible (e.g., due to unstable medical condition).
 - Patients who cannot undergo an MRI/MRA/MRP will undergo a multimodal CT/CTA/CTP instead.

Occurrence of an ICH event within 36 hours:

- *In the event of an ICH event that occurs within 36 hours of drug administration, a NIHSS assessment is to be completed (see Appendix 3 for the NIHSS)*

72–96 hour imaging:

- The second MRI will be obtained at 72–96 hours after randomization and will only include FLAIR, GRE, and DWI for assessment of final infarct volumes.
 - *Patients who cannot undergo a MRI will undergo a non-contrast CT*

Appendix 8

Modified Thrombolysis in Cerebral Infarction (TICI) Scale

Table 1 presents the Modified Thrombolysis in Cerebral Infarction (TICI) scale as it is currently adopted for emergent large vessel occlusion (ELVO).

Table 1. Modified Thrombolysis in Cerebral Infarction (TICI) Scale

Scale	Description
0	No perfusion or anterograde flow beyond site of occlusion

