2.2.3 Exploratory Efficacy Endpoints

The following exploratory efficacy endpoints will be analyzed:

- Median final infarct volumes at 72-96 hours visit or discharge (if patient is being discharged prior to 72-96 hours visit).
- Median infarct growth at 72-96 hours visit or discharge (if patient is being discharged prior to 72-96 hours visit).
- Ordinal mRS score at Day 90 by occlusion type (M1/ICA or M2 occlusions).
- Ordinal mRS score at Day 30 and Day 90 by randomization site (ECC or nECC).
- Proportion of patients who are randomized at an nECC and transferred to an ECC for endovascular therapy for whom planned thrombectomy was not performed.
- Proportion of patients readmitted within 30 days from discharge.
- Proportion of patients requiring one pass with endovascular therapy device (endovascular patients only).
- Mean Quality of Life in Neurological Disorders (Neuro-QoL) scores by domain.
- Proportion of patients where planned thrombectomy was not performed.
- Overall survival at Day 90.

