4.6.3.2 Final Infarct Volumes and Infarct Growth

Two follow-up imaging scans will be obtained after randomization, one at 24±6 hours and one at 72-96 hours (or discharge if patient is being discharged prior to 72-96 hours visit) after study drug administration. The scan at 72-96 hours visit (or discharge if patient is being discharged prior to 72-96 hours visit) will be used to evaluate the final infarct volume (captured as infarct volume on CT scan page and diffusion-weighted imaging (DWI) lesion volume on MRI scan page). Infarct growth will be defined as change from baseline at 72-96 hours visit (or discharge if patient is being discharged prior to 72-96 hours visit) in infarct volume. Patient who died before 72-96 hours visit and were not discharged prior to death will be excluded from the analysis.

Final infarct volumes and infarct growth at 72-96 hours visit assessment or discharge will be summarized descriptively (mean, median, etc.) and analyzed with nonparametric methods. The van Elteren's test will be used to produce p-values for the comparison of the distribution of tenecteplase versus placebo arms, adjusting as specified in Section 4.6. The median treatment differences will be presented with 95% CI based on the Hodges-Lehmann approach for the location shift (median treatment difference).

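### SAP Table 2's imaging windows contradict the discharge-scan definition of the two infarct endpoints for discharges before 60 h, and in-hospital deaths before the visit are excluded with no sensitivity analysis

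*SAP*

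**What the plan says.** **Endpoint.** SAP 2.2.3 lists "Median final infarct volumes at 72-96 hours visit or discharge (if patient is being discharged prior to 72-96 hours visit"), and defines infarct growth in the same way. SAP 4.6 repeats the discharge alternative for growth. SAP 4.6.3.2 is explicit about the source: "The scan at 72-96 hours visit (or discharge if patient is being discharged prior to 72-96 hours visit) will be used" to evaluate final volume. None of these places sets an earliest time for a discharge scan.

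**Windows.** In SAP Table 2 the imaging window is 18-30 h for the 24 h visit and "60 to 120 hours" for the 72-96 h visit. The text above the table says: "Assessments that are outside of the defined windows will not be used in analysis". The one exception lets an out-of-window mRS be carried forward.

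**Scan waiver.** Protocol Appendix 1, footnote p (repeated in SAP Appendix 2), allows the 72-96 h activities to be done at discharge. It then waives the later image altogether: "If the patient is discharged within 24 hours of the 24-hour visit", none is required.

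**Deaths.** SAP 4.6.3.2: "Patient who died before 72-96 hours visit and were not discharged prior to death will be excluded from the analysis". SAP 4.9 leaves missing values missing unless stated otherwise, and every sensitivity analysis in SAP 4.6.4 concerns the primary endpoint.

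**Method.** The van Elteren test, with a Hodges-Lehmann shift and 95% CI.

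**The concern.** Two rules in one SAP give different datasets for the same endpoint. A programmer who follows 4.6.3.2 keeps a discharge scan at 50 h; one who follows Table 2 drops it. A plan should settle that before unblinding.

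The contradiction sits beside two other routes out of the analysis, the scan waiver and the death exclusion. Early discharge and early death both plausibly relate to infarct size, and either could be affected by treatment. If so, the analysed patients are a selected part of the ITT population in which SAP 4.1.1 says all efficacy analyses are done. The SAP handles death differently elsewhere: it is scored 6 on the mRS and 5 on the reversed GOS, so those patients stay in.

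**Working it through.** The documents state no sample size, power or expected loss for these endpoints, so there is no planned figure to reproduce. The check is an interval comparison, followed by an illustration on assumed inputs.

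**1. Discharge scans against Table 2** (hours after randomisation)

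| Time of discharge scan | Table 2 imaging row | Result if Table 2 governs |
|---|---|---|
| 18 to 30 h | 24 h visit | not available as the 72-96 h value |
| over 30 to under 60 h | none | not used |
| 60 to under 72 h | 72-96 h visit | kept |

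**2. Adding the footnote p waiver.** The scan is not required for discharge up to 24 h after the 24 h visit, which itself may fall at 18-30 h.

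| 24 h visit at | Scan waived up to | Required but dropped | Required and kept | Dropped share of required time |
|---|---|---|---|---|
| 18 h | 18 + 24 = 42 h | 42-60 h (18 h) | 60-72 h (12 h) | 18/30 = 60% |
| 24 h | 24 + 24 = 48 h | 48-60 h (12 h) | 60-72 h (12 h) | 12/24 = 50% |
| 30 h | 30 + 24 = 54 h | 54-60 h (6 h) | 60-72 h (12 h) | 6/18 = 33% |

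These are shares of clock time, not of patients. Table 2 can remove a required scan only in the 6 to 18 hours before 60 h. Before that, a missing scan comes from the waiver, although a scan taken voluntarily would also fall foul of the window.

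**3. Illustration; every input is assumed.** Volumes V are lognormal with placebo median 30 mL and log-SD 1.2; the tenecteplase median is 0.8 × 30 = 24 mL, a true difference of -6.0 mL. With z = (ln V - ln 30)/1.2, logit P(lost to early discharge) = a - 1.5z and logit P(early death) = b + 1.5z. The constants a and b give 10% or 20% early discharge (window and waiver together) and 5% early death in placebo.

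| Loss applied | Median difference, 10% discharged | Median difference, 20% discharged |
|---|---|---|
| Early discharge only | -6.1 mL | -6.3 mL |
| Early death only | -5.3 mL | -5.3 mL |
| Both | -5.3 mL | -5.5 mL |

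Simulation error is up to about 0.1 mL. With both losses, 15% to 25% of placebo patients are lost and the placebo median reads 31.9 or 35.9 mL instead of 30 (31.9/30 = 1.06; 35.9/30 = 1.20). The SAP's own estimator, the Hodges-Lehmann shift, moves from about -4.3 mL to about -3.9 mL (10%) or -4.2 mL (20%). With a weaker slope of 0.5 and both losses, the median difference is -6.0 or -6.3 mL, so it does not shrink.

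In this model the shrinkage in the median difference comes from the death exclusion. Losing early discharges alone does not shrink it, although the ratio of medians does move, from 0.80 to 0.82-0.84. The direction depends on the slope, on which loss dominates and on the summary measure.

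**The case against.** The strongest reply is that the SAP does not intend to drop these scans. The endpoint-specific text in 4.6.3.2 says the discharge scan is used, 2.2.3 and 4.6 agree with it, 4.6 includes available data regardless of adherence, and the windows are introduced as applying to clinical efficacy assessments. This stands in part: exclusion is not certain. It does not remove the contradiction. Table 2 has its own imaging column, the only exception written is for mRS, and nothing says that 4.6.3.2 takes precedence.

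On deaths, a 72-96 h volume does not exist for a patient who has died, and the exclusion is disclosed. Death and haemorrhage are also reported through the mRS, survival, sICH, mortality and PH2. That is fair, and the exclusion can stay in the main analysis. What is missing is any check of how much it matters.

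A third reply concerns the remedy. One could take the 18-30 h scan as the final volume whenever nothing later exists; Protocol Appendix 7 says it is obtained "to assess reperfusion, recanalization, and ischemic core growth". But that redefines a final volume and makes the time of measurement depend on discharge or death. Nor do the documents confirm that infarct volume is centrally read on those scans. It belongs in a sensitivity analysis.

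**Conclusion.** The contradiction is real and follows from the text alone: for discharge before 60 h, Table 2 and 4.6.3.2 cannot both be followed. Together with the scan waiver and the unexamined death exclusion, it means inclusion in these two endpoints may depend on outcome.

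Four stronger readings are tempting, and the documents do not support them:

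- **Table 2 discards discharge scans as a class.** Those at 60-72 h are inside the window, and the earliest discharges may have no scan to discard.
- **Nobody discharged before 60 h contributes.** That holds only if Table 2 overrides 4.6.3.2, which the SAP does not say.
- **The best and worst patients are removed.** This is a reasonable clinical inference, but the documents do not tie early discharge to small infarcts. The exclusion also covers only deaths before the visit without prior discharge.
- **The treatment effect is biased towards zero by a known amount.** No early-discharge or early-death rate is given, and the illustration changes direction with its assumptions.

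Both endpoints are exploratory and outside the SAP Table 3 hierarchy. The primary test, the secondary tests and the type I error are unaffected.

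**What to change.** 1. Add to SAP Table 2 or 4.6.3.2 that, for a patient discharged before the 72-96 h visit, the discharge scan is mapped to that visit for final infarct volume and infarct growth, regardless of the 60 h lower limit.
2. Report by arm how many patients are missing from each endpoint because of the window (if any remain), the footnote p waiver, and death before the visit.
3. Add a sensitivity analysis that includes patients without a qualifying scan: for example, worst rank for early deaths, or the 18-30 h scan as a fallback where a central volume is available.

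The cost is a sentence in the SAP, one derivation, one table and one extra analysis, with no new data collection. Using the 18-30 h scan may need volume reads on images already sent to the central reader. The drawback is that some analysed volumes will be measured sooner after the stroke than others.

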6.4.1 Primary Efficacy Endpoint

The primary endpoint is the ordinal mRS score at Day 90. The distribution of the mRS scores will be compared between the treatment groups by a proportional odds model controlling for the randomization strata *and baseline mechanical thrombectomy planned status*. If the proportional-odds assumptions are not met, alternative assumption-free ordinal analysis on the mRS score will be used (Agresti 1980; Howard et al. 2012; Churilov et al. 2014). Further details about the assumption-free method will be described in the SAP. Superiority of tenecteplase over placebo will be declared if the p-value of the estimated treatment effect from the proportional odds model is ≤ 0.049 (two-sided). An unadjusted analysis will also be performed using the Wilcoxon-Mann-Whitney test.

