2.3 DETERMINATION OF SAMPLE SIZE

Approximately 456 patients will be enrolled in this study. Assuming the distribution of mRS scores at Day 90 in the two treatment arms as shown in [Table 1](#) and a 5% dropout rate in the study, approximately 228 patients in each treatment group will provide at least 90% power to detect the specified difference in the distribution of the mRS scores at the 2-sided 0.049 significance level (after adjustment for one efficacy interim analysis). This corresponds to being able to detect a common odds ratio (OR) of at least 1.76 (tenecteplase vs. placebo), with a total sample size of approximately 432 evaluable patients, assuming a 5% dropout rate.

Table 1 Assumed Distribution of 90-Day mRS in Use in Sample Size Determination

mRS	0	1	2	3	4	5	6
Tenecteplase (% of patients)	17	20	16	15	13	7	12
Placebo (% of patients)	13	13	12	14	18	12	18

mRS = modified Rankin Scale

The sample size estimation is highly dependent on the distribution assumption of 90-day ordinal mRS score for both treatment arms; thus, additional power calculation were performed with 456 total patients, assuming 5% drop-out rate, for different distribution scenarios on the mRS at Day 90, derived from previous stroke studies. These resulted in >88% and >99% power to detect the specified difference in the distribution of the mRS scores. For more details, see Section 6.1 of the Protocol.

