4.9.1.2 Multiple Imputation

Missing mRS data will be imputed using a sequential regression method. Particularly, mRS will be sampled from a multinomial distribution. This distribution will be estimated by ordinal logistic regressions, using baseline covariates and the previous mRS value.

The ordinal logistic regressions estimate the cumulative odds for achieving an mRS outcome of at most k :

$$\text{logit}[\Pr(mRS_t \leq k)] = \alpha_{kt} + X\beta_t + mRS_{t-1}\delta_t$$

where t is the time point index (Day 5, Day 30, Day 90), $k = 0$ to 5 , α_{kt} are intercepts, X is the design matrix for the baseline covariates and β_t are the corresponding regression coefficient vectors, and mRS_{t-1} is the previous mRS result (baseline, Day 5 or hospital discharge, or Day 30) with its coefficient δ_t . The list of covariates will include age, sex, race (white vs. non-white), baseline NIHSS, occlusion type and discharge destination (home vs. non-home).

Separate regressions will be fitted for each treatment group to avoid any assumptions about the treatment effect. In order to limit the number of parameters and prevent estimation issues, it will be assumed that the covariate effects β_t and δ_t do not depend on k (the proportional odds assumption). The model may be revised if estimation issues are encountered (e.g. quasi-complete separation). Logit is the usual link transformation, associated with a logistic regression.

For each fixed value of Δ , imputation is carried out in the following steps. These steps are repeated to impute missing mRS first at Day 30, then at Day 90 (using imputed Day 30 results):

- Fit the ordinal logistic regressions for mRS at time t , separately in the TNK and placebo groups.
- For patients with missing mRS at time point t , obtain the predicted cumulative probabilities. In the placebo group, use the probabilities predicted by the model. In the TNK group, recalculate the probabilities using the following equation.

$$\text{logit}[\Pr(mRS_t \leq k)] = \widehat{\alpha}_{kt} + X\widehat{\beta}_t + mRS_{t-1}\widehat{\delta}_t - \Delta$$

where $\widehat{\alpha}_{kt}$, $\widehat{\beta}_t$ and $\widehat{\delta}_t$ are the estimated coefficients from the TNK model. The penalty term Δ reduces the odds for a favorable outcome. This penalty will only be applied the first time mRS is missing for the patient; its effect will be propagated to subsequent time points by the mRS_{t-1} term in the regression.

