$$\hat{\sigma}^2 = \left\{ \frac{1}{N_1} \sum_j P_{1j} \left(\hat{\alpha} \sum_{i<j} P_{2i} - \sum_{i>j} P_{2i} \right)^2 + \frac{1}{N_2} \sum_j P_{2j} \left(\hat{\alpha} \sum_{i>j} P_{1i} - \sum_{i<j} P_{1i} \right)^2 \right\} / \left(\sum_{i>j} P_{1i} P_{2j} \right)^2$$

The more accurate confidence interval is derived for $\log(\hat{\alpha})$ and then exponentiated:

$$\exp(\log(\hat{\alpha}) \pm \frac{Z_{0.025} \hat{\sigma}}{\hat{\alpha}})$$

3. For the stratified analysis, derive these statistics separately for each stratum ($m=1, \dots, M$) to arrive at $\hat{\alpha}_m$ and $\hat{\sigma}_m$. The following formulas can be used to estimate $\log(\hat{\alpha})$ and its variance:

$$\log(\hat{\alpha}) = \sum_m \hat{\alpha}_m^2 \log \hat{\alpha}_m / \hat{\sigma}_m^2 / \sum_m \hat{\alpha}_m^2 / \hat{\sigma}_m^2$$

$$\widehat{Var}(\log(\hat{\alpha})) = \left(\sum_m \hat{\alpha}_m^2 / \hat{\sigma}_m^2 \right)^{-1}$$

Appendix 5

Selection of Adjusting Variables

This appendix presents the algorithm for selecting the variables to adjust efficacy analyses, starting from the initial list identified in section 4.6, excluding the protocol version variable.

- V1: Age (≤ 70 vs. > 70 years of age)
- V2: Type of occlusion (ICA/M1 vs. M2)
- V3: Baseline NIHSS (≤ 15 vs. > 15)
- V4: Randomization site (ECC vs. nECC)
- V5: Mechanical thrombectomy planned (Yes vs. No)

By default, the protocol version variable will be included in the model. Only if it is impossible to meet the minimum cell size requirement, the protocol version variable will be added to the above list as V6, and the variable selection algorithm will be repeated for all six variables.

A combination of variables C_i is any subset of these variables, i runs from 1 to 2^5 . For example, (V1, V2, V5) selects Age, Type of Occlusion and MT Planned.

The combination's length L_i is the number of variables it includes. For the example of (V1, V2, V5), $L_i = 3$.

The combination's smallest cell size S_i is the smallest number of observations among 2^{L_i+1} cells formed by crossing all of the combination's variables and treatment. For the example of (V1, V2, V5), there are 16 cells to evaluate. If there are empty cells, $S_i = 0$.

The algorithm is applied to the dataset with non-missing outcome and adjusting variables, and proceeds as follows:

- (1) Calculate L_i and S_i for $i=1$ to 2^5 .

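### Using age and baseline NIHSS only as two-level cuts gives up a small amount of power in the primary model and in six secondary models

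*SAP*

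**What the plan says.** SAP 4.6 introduces its adjustment list with "Analyses will be adjusted for all or a subset of the following variables". Age appears only as up to 70 versus over 70 years, and baseline NIHSS only as up to 15 versus over 15 points. They stand beside occlusion type, site type, planned thrombectomy and protocol version. SAP Appendix 5, which decides which variables survive, carries the same form, for example "V3: Baseline NIHSS (≤ 15 vs. > 15". Under Protocol 6.4.1 the mRS distribution is "compared between the treatment groups by a proportional odds model controlling for the randomization strata", together with planned thrombectomy status. The sample code in SAP Appendix 3 enters the stratification factors as class variables.

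Six of the seven secondary endpoints are analysed by logistic regression with the 4.6 list (SAP 4.6.2.1–4.6.2.4, 4.6.2.6 and 4.6.2.7). Day 90 NIHSS (4.6.2.5) uses van Elteren's test.

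Both variables exist as numbers. SAP 4.6.2.5 describes an NIHSS total of 0 to 42, Protocol 4.5.2 records age, and SAP 4.6.5 cuts age at 80 for a subgroup. The imputation model for the tipping point names them without cut points: "The list of covariates will include age, sex, race (white vs. non-white), baseline NIHSS, occlusion type and discharge destination (home vs. non-home". The model then fitted to the imputed data returns to the stratification factors (Appendix 3). No sensitivity analysis in SAP 4.6.4 uses either variable as a number in the outcome model.

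**The concern.** The cuts exist to balance randomisation; the outcome model does not have to keep them. As written, a patient with NIHSS 6 is treated like one with 15, and a 71-year-old like a 95-year-old. If age and severity predict Day 90 mRS, the variation within each half goes unused.

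What is at stake is power in the primary test and in the logistic endpoints. Functional independence is first in the SAP Table 3 hierarchy and testing stops at the first p-value above 0.049, so its power matters for every endpoint below it.

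**Working it through.** **1. The plan's own figure.** Inputs from SAP 2.3: "at the 2-sided 0.049 significance level (after adjustment for one efficacy interim analysis"), "will provide at least 90% power to detect the specified difference in the distribution of the mRS scores", "being able to detect a common odds ratio (OR) of at least 1.76", 216 evaluable patients per arm, and Table 1 ("Assumed Distribution of 90-Day mRS in Use in Sample Size Determination"). The Protocol synopsis names the Wilcoxon-Mann-Whitney test.

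- Probability that a tenecteplase patient does better than a placebo patient, ties counted half: 0.17×0.935 + 0.20×0.805 + 0.16×0.68 + 0.15×0.55 + 0.13×0.39 + 0.07×0.24 + 0.12×0.09 = 0.58955.
- Pooled proportions 0.15, 0.165, 0.14, 0.145, 0.155, 0.095, 0.15 give Σp³ = 0.0216. Null SE = √[(1 − 0.0216)/12 × (1/216 + 1/216)] = 0.02748.
- z = 0.08955/0.02748 = 3.259. With critical value 1.969, power = Φ(1.291) = 90.2%. With the variance under the alternative it is 90.5%.
- Cross-check, Whitehead formula at OR 1.76: SE = √[12/(432 × 0.9784)] = 0.1685, z = 0.5653/0.1685 = 3.355, power 91.7%.

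The stated 90% is reproduced with no covariates at all.

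**2. Cuts against numbers.** Large-sample fits: 300,000 simulated patients, standard errors rescaled to N = 432, placebo mRS as in Table 1, marginal OR 1.76, two-sided alpha 0.049. Assumptions, none of them in the documents: age about normal, mean 70, SD 13; NIHSS 5 or more, right-skewed, mean 13, SD 6; linear effects on the logit scale. The models contain treatment, age and NIHSS only. Relative efficiency (RE) = (z with numbers / z with cuts)², and patient equivalent = 432 × (RE − 1). The second decimals are kept only so that the differences can be followed.

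| Assumed OR per SD, age / NIHSS | Primary power, cuts → numbers (%) | RE | Patients | mRS 0–2 power, cuts → numbers (%) | RE |
|---|---|---|---|---|---|
| 1.00 / 1.00 | 91.17 → 91.17 | 1.00 | 0 | 82.54 → 82.53 | 1.00 |
| 1.22 / 1.35 | 91.95 → 92.38 | 1.02 | 8 | 82.88 → 83.23 | 1.01 |
| 1.35 / 1.65 | 93.09 → 93.85 | 1.04 | 15 | 83.18 → 83.91 | 1.02 |
| 1.65 / 2.01 | 94.39 → 95.90 | 1.09 | 37 | 84.73 → 86.27 | 1.05 |
| 1.82 / 2.46 | 95.50 → 97.36 | 1.14 | 59 | 85.84 → 88.20 | 1.08 |

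Fourth data row written out: with cuts, OR 1.8395 and SE 0.1714, so z = 3.557; with numbers, OR 1.8949 and SE 0.1724, so z = 3.708. RE = (3.7076/3.5567)² = 1.087, and 432 × 0.087 ≈ 37. The SE rises slightly; the gain comes from the larger conditional log odds ratio.

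Changing the distributions (age 72, SD 14; NIHSS 12, SD 5) in that row gives RE 1.09. Other assumed strengths with the actual cuts gave 1.01 to 1.11. Adding the SAP's other factors, with occlusion type assumed correlated with NIHSS, gave a gain of 3% at log odds ratios of 0.35 and 0.5 per SD.

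**3. Type I error.** In 1,500 simulated trials per setting at nominal 4.9%, rejection was 4.8–5.6% with cuts and 5.1–5.5% with numbers. The Monte Carlo SE is √(0.049 × 0.951/1,500) = 0.56 points, so neither shows inflation.

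**4. The proportional-odds check.** SAP 4.6.1 sends the primary analysis to the stratified generalised odds ratio unless the overall score test gives p > 0.05, and that test includes the adjusting variables. In simulated trials with all six SAP covariates (N = 432, 500 per setting, assumed log odds ratios 0.5 and 0.7 per SD), the check rejected about as often either way when odds were proportional (6% and 5%). When the age effect varied across mRS thresholds, numbers in place of cuts raised rejection from 9% to 15% (mild) and from 26% to 48% (stronger). That non-proportionality is assumed.

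**5. Appendix 5.** Five two-level variables crossed with treatment make 2⁶ = 64 cells, on average 432/64 = 6.75 patients, against a threshold of 1% of 456 = 4.56. Age or NIHSS could therefore be dropped. Linear terms form no cells. The three remaining factors make 2⁴ = 16 cells, on average 27 patients.

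**The case against.** Adjusting for the stratification factors is standard and agrees with Protocol 6.4.1. The power claim rests on an unadjusted test, so nothing promised is missed, and the cuts already add power: 91.2% unadjusted in the same simulations against 91.9–95.5% with cuts. All of this stands, and it makes the point one of efficiency and not of error.

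The strongest practical objection is the proportional-odds check. If linear terms entered it, non-proportionality in age or NIHSS could push the primary analysis to a fallback that cannot use them, which would defeat the purpose. This also stands, and the fix has to deal with it.

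It is also fair that the size is uncertain and that the reported odds ratio would change, because it would be conditional on the continuous covariates.

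**Conclusion.** The point holds as a modest, cheap gain in power: 0.4 to 1.9 points in the primary model and about 0.4 to 2.4 points for mRS 0–2, under the assumptions in the working. If age and NIHSS had no prognostic effect, the gain would be nil.

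Three stronger readings are tempting and are not supported.

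- *The trial is underpowered or its primary test invalid.* The 90% figure is reproduced without covariates, and the type I error is sound with either form.
- *Every efficacy test loses precision.* In these models the standard error does not shrink with numbers. Van Elteren's test, the stratified log-rank test and the stratified fallback need strata, so the cuts belong there.
- *The loss is large.* The familiar result that a cut keeps about 64% of the information applies to a normal covariate cut near its median. The documents give no distribution, entry requires NIHSS of at least 5, and nothing shows that 15 is near the median. Median cuts with assumed log odds ratios as high as 0.7 and 1.1 per SD give a gain of 17%, about 74 patients, but the documents offer no support for those values.

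**What to change.** Before unblinding and by blinded staff, amend SAP 4.6, Appendices 3 and 5, and Protocol 6.4:

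- Enter age (years) and baseline NIHSS (points, baseline as defined in SAP 4.3) as linear terms in the proportional-odds and logistic models. Keep occlusion type, site type, planned thrombectomy and protocol version as factors.
- Leave the linear terms outside the Appendix 5 cell count. For these models the selection rule then starts from the other factors.
- Keep the proportional-odds check in SAP 4.6.1 on the model with two-level factors, and say so, since it then no longer tests the linear terms.
- Leave van Elteren's test, the stratified log-rank test and the stratified generalised odds ratio on the two-level strata.
- State which model the interim (0.003) and the final analysis (0.049) each use. Protocol 6 requires the SAP to be final before the interim data-cut; if the interim has already used the cuts, record the change as applying to the final analysis.

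Pre-stroke mRS and core volume need not be added: the first is restricted to 0–2 by the entry criteria, and the second comes from different imaging methods.

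The cost is wording and revised model statements, with no new data or patients. The downsides are an assumed roughly linear effect on the logit scale, where misfit would give back some of the gain, and an odds ratio that must be reported as conditional on the continuous covariates.
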